### eHealth Literacy Scale

**The following questions are about your opinion and experiences using the internet for health information. For each statement, tell me which response best reflects your opinion and experience *right now*.**

1. How **useful** do you feel the Internet is in helping you in making decisions about your health?

 1	 2	 3	 4	 5
Not useful at all	Not useful	Unsure	Useful	Very Useful

2. How **important** is it for you to be able to access health resources on the Internet?

 1	 2	 3	 4	 5
Not important at all	Not important	Unsure	Important	Very important

3. I know **what** health resources are available on the Internet.

- 1)  Strongly Disagree
- 2)  Disagree
- 3)  Undecided
- 4)  Agree
- 5)  Strongly Agree

4. I know **where** to find helpful health resources on the Internet.

- 1)  Strongly Disagree
- 2)  Disagree
- 3)  Undecided
- 4)  Agree
- 5)  Strongly Agree

5. I know **how** to find helpful health resources on the Internet.

- 1)  Strongly Disagree
- 2)  Disagree
- 3)  Undecided
- 4)  Agree

5)  Strongly Agree

6. I know **how to use** the Internet to answer my questions about health.

- 1)  Strongly Disagree
- 2)  Disagree
- 3)  Undecided
- 4)  Agree
- 5)  Strongly Agree

7. I know how to use **the health information** I find on the Internet to help me.

- 1)  Strongly Disagree
- 2)  Disagree
- 3)  Undecided
- 4)  Agree
- 5)  Strongly Agree

8. I have the skills I need to **evaluate** the health resources I find on the Internet.

- 1)  Strongly Disagree
- 2)  Disagree
- 3)  Undecided
- 4)  Agree
- 5)  Strongly Agree

9. I can tell **high quality** health resources from **low quality** health resources on the Internet.

- 1)  Strongly Disagree
- 2)  Disagree
- 3)  Undecided
- 4)  Agree
- 5)  Strongly Agree

10. I feel **confident** in using information from the Internet to make health decisions.

- 1)  Strongly Disagree
- 2)  Disagree
- 3)  Undecided
- 4)  Agree
- 5)  Strongly Agree

**Need for Cognition Scale (from Cacioppo, Petty, & Kao, 1984)**

For each of the statements below, please indicate whether or not the statement is characteristic of you or of what you believe. For example, if the statement is extremely uncharacteristic of you or of what you believe about yourself (not at all like you) please place a "1" on the line to the left of the statement. If the statement is extremely characteristic of you or of what you believe about yourself (very much like you) please place a "5" on the line to the left of the statement. You should use the following scale as you rate each of the statements below.

1 extremely uncharacteristic of me	2 somewhat uncharacteristic of me	3 uncertain	4 somewhat characteristic of me	5 extremely characteris of me
---	--	----------------	--	--

1. \_\_\_\_\_ I would prefer complex to simple problems.
2. \_\_\_\_\_ I like to have the responsibility of handling a situation that requires a lot of thinking.
3. \_\_\_\_\_ Thinking is not my idea of fun.\*\*
4. \_\_\_\_\_ I would rather do something that requires little thought than something that is sure to challenge my thinking abilities.\*\*
5. \_\_\_\_\_ I try to anticipate and avoid situations where there is a likely chance I will have to think in depth about something.\*\*
6. \_\_\_\_\_ I find satisfaction in deliberating hard and for long hours.
7. \_\_\_\_\_ I only think as hard as I have to.\*\*
8. \_\_\_\_\_ I prefer to think about small daily projects to long term ones.\*\*
9. \_\_\_\_\_ I like tasks that require little thought once I've learned them.\*\*
10. \_\_\_\_\_ The idea of relying on thought to make my way to the top appeals to me.
11. \_\_\_\_\_ I really enjoy a task that involves coming up with new solutions to problems.
12. \_\_\_\_\_ Learning new ways to think doesn't excite me very much.\*\*
13. \_\_\_\_\_ I prefer my life to be filled with puzzles I must solve.
14. \_\_\_\_\_ The notion of thinking abstractly is appealing to me.

Fertilit-e  
Wake Forest Baptist Comprehensive Cancer Center (WFBCCC)  
WFBCCC # 01717

15. \_\_\_\_\_ I would prefer a task that is intellectual, difficult, and important to one that is somewhat important but does not require much thought.
16. \_\_\_\_\_ I feel relief rather than satisfaction after completing a task that requires a lot of mental effort.\*\*
17. \_\_\_\_\_ It's enough for me that something gets the job done; I don't care how or why it works.\*\*
18. \_\_\_\_\_ I usually end up deliberating about issues even when they do not affect me personally.

Note: \*\*=reverse scored item.

**Please see IRB for Fertilit-e Alpha Testing Interview Guide 8.27.18**

**System Usability Scale**

For the next questions, please read each sentence and rate your level of agreement.

		Strongly disagree			Strongly agree
1	I think that I would like to use Fertilit-e frequently (when thinking about my fertility options)	1	2	3	4
2	I found Fertilit-e unnecessarily complex	1	2	3	4
3	I thought Fertilit-e was easy to use	1	2	3	4
4	I think that I would need the support of a technical person to be able to use Fertilit-e	1	2	3	4
5	I found the various functions in Fertilit-e were well integrated	1	2	3	4
6	I thought there was too much inconsistency in Fertilit-e	1	2	3	4
7	I would imagine that most people would learn to use Fertilit-e very quickly	1	2	3	4
8	I found Fertilit-e very cumbersome to use	1	2	3	4
9	I felt very confident using Fertilit-e	1	2	3	4
10	I needed to learn a lot of things before I could get going with Fertilit-e	1	2	3	4
11	Compared to reading a brochure, I liked using Fertilit-e more.	1	2	3	4

12. Overall, would you rate the user-friendliness of Fertilit-e as:

- Excellent
- Good
- OK
- Poor
- Awful

Fertilit-e

Wake Forest Baptist Comprehensive Cancer Center (WFBCCC)

WFBCCC # 01717

Brooke J. SUS-A quick and dirty usability scale. Usability evaluation in industry.  
1996;189(194):4-7.

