## **6.0 Analytic Plan**

### **6.1 Analysis of Primary Outcome**

Q-PRO staff will review qualitative data to provide an integrative summary and identification of key points, potential themes, and areas of further exploration. A summary report will be created using the interview recordings and interviewer field notes. The report would include a summary for each module based on the data from the Think Aloud and Interview Guide that incorporates usability for Fertilit-e alpha. Q-PRO will also include a section on general comments and overall recommendations. Finally, they will be maintaining a spreadsheet that includes data for the sequence of modules selected, modules skipped, and overall time spent using the app. Q-PRO will then move to standard analysis (transcription, thematic analysis, saturation, etc.) for beta testing.

Our study team will calculate descriptive statistics for the System Usability Scale by gender and race/ethnicity.

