### 6.3 Analysis of Exploratory Outcomes

We will calculate descriptive statistics (means and standard deviations, frequencies) for all sociodemographic variables, the health literacy scale, the technology use items, the eHealth literacy scale, and the Need for Cognition – short form^34 to describe the study population. This will be considered exploratory due to the small sample size and intentional selection of participant groups.

To explore differences in usability by health literacy, sociodemographic characteristics, technology use and eHealth literacy, we will use t-tests, ANOVAs, and correlations to examine the relationship between these variables and the outcome of the System Usability Scale score.

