### 6.4 Sample Size and Power

The combined sample size from each round of computer prototype testing (N=24) should permit us to achieve data saturation for gender (12 men and 12 women). With 24 participants, we will also be able to estimate the usability data within  $\pm 0.4$  SD for the System Usability Scale using 2-sided 95% confidence intervals (CIs).

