**APPENDIX C. Data Collection Measures**

Variable/Construct	Measure	Items	Source
Health Literacy	Brief Health Literacy Screener	3	Chew et al., 2008; Wallston et al., 2014
Patient Characteristics	Sociodemographic variables	23	Standard items
Technology Use	Type, frequency, and purpose of technology use variables	11	Study team developed
eHealth Literacy	Questions about comfort with and use of eHealth information	10	Norman & Skinner, 2006
Need for Cognition	Need for Cognition Scale	18	Cacioppo et al., 1984
Comprehensibility	Interview Guide	10	Study team developed and informed by Kelly-Blake et al., 2014
Usability	Interview Guide; System Usability Scale	11; 12	study team developed; Brooke, 1996

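### Does the lack of a stated scoring rule stop the System Usability Scale form from giving a usable score?

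*Combined protocol and SAP*

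**What the plan says.** The SUS is used in three places.

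- Section 6.1: "Our study team will calculate descriptive statistics for the System Usability Scale by gender and race/ethnicity".
- Section 6.3: t-tests, ANOVAs and correlations are to "examine the relationship between these variables and the outcome of the System Usability Scale score".
- Section 6.4: "With 24 participants, we will also be able to estimate the usability data within" ±0.4 SD, using two-sided 95% confidence intervals.

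None of these sections says which items enter the score, which are reversed, or how the total is scaled.

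In the Appendix C measures table, the usability row reads "Interview Guide; System Usability Scale", with item counts of 11 and 12 respectively. The SUS is credited to one published source. On the form itself, items 1-11 are agreement ratings, shown with options 1 to 4 in the text available. Items 2, 4, 6, 8 and 10 are worded negatively. Item 11 is "Compared to reading a brochure, I liked using Fertilit-e more". Item 12, "Overall, would you rate the user-friendliness of Fertilit-e as", has five verbal categories running from best to worst.

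**The concern.** Section 6.3 treats "the outcome of the System Usability Scale score" as a single number, yet the 12 items counted under that name do not share a response format or a direction. Item 12 cannot simply be added to the others. Item 11 asks for a preference over a brochure, which is arguably a different construct from ease of use. No instruction says that the five negative items must be turned round, although the Need for Cognition form in the same appendix marks its reversed items.

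The stake is whether the score measures usability at all. It is the only scored usability scale in the study. If it were summed as printed, a good tool and a poor one would look almost alike. If a conversion designed for a different number of response options were used, the point scores would be distorted.

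**Working it through.** **Inputs.** N = 24 and ±0.4 SD (Section 6.4). Item wording, order and response options come from the SUS form in Appendix C. Options 1 to 4 are taken as they appear there.

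**1. The plan's own figure.** The half-width of a 95% interval for a mean, in SD units, is 1.96/√N.

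1.96/√24 = 1.96/4.899 = 0.400, which reproduces the stated ±0.4 SD. With the t quantile on 23 degrees of freedom it is 0.422. The score's own SD is the unit, so the figure is the same whatever scoring rule is used.

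**2. Extreme respondents under different rules.** The most favourable respondent answers 4 to each positive item and 1 to each negative item. The least favourable does the opposite.

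| Rule | Most favourable | Least favourable |
|---|---|---|
| Items 1-10, no reversal | 5×4 + 5×1 = 25 | 5×1 + 5×4 = 25 |
| Items 1-11, no reversal (possible range 11-44) | 25 + 4 = 29 | 25 + 1 = 26 |
| Items 1-12, item 12 coded Excellent = 1, Awful = 5 | 29 + 1 = 30 | 26 + 5 = 31 |
| Items 1-12, item 12 coded Excellent = 5, Awful = 1 | 29 + 5 = 34 | 26 + 1 = 27 |
| Items 1-10, negative items reversed, rescaled | 100 | 0 |

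The last row uses S = Σ(odd item − 1) + Σ(4 − even item), which runs from 0 to 30, and then 100 × S/30. The naive sums fail, but the same answers yield a fully discriminating score once the negative items are reversed.

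**3. Error of scaling only.** Suppose, purely as an assumption because the documents give no conversion, that a formula built for options 1 to 5 were applied to answers of 1 to 4: (odd − 1) and (5 − even), summed and multiplied by 2.5. Each of the five even items then contributes one extra point:

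score = 2.5 × (S + 5) = 12.5 + 2.5S.

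The correctly scaled score is X = 100S/30, so 2.5S = 0.75X and the score is 12.5 + 0.75X. The range becomes 12.5 to 87.5, and a group difference in points shrinks by 25%. The SD is also multiplied by 0.75. In a t-test the factor cancels: (0.75 × difference)/(0.75 × SE) = difference/SE. The same holds for F statistics, and correlations are unchanged by a positive linear transformation. Only the point summaries in Section 6.1 would move.

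**4. Does any text plan the faulty sum?** The measures table reports how many items each instrument contains; it is not a scoring definition. Sections 6.1, 6.3 and 6.4 refer to the scale by name. None calls for a 12-item total or for adding items without reversal.

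**The case for a change.** The strongest case for acting is that the scoring rule decides whether the number means anything (25 against 25, or 100 against 0), while writing it down costs one sentence. The measures table puts all 12 items under one citation without marking any as additions, and the authors recorded scoring direction for Need for Cognition but not for the scale they analyse as an outcome. The four-option grid also looks genuine: every row ends at 4, and the right-hand anchor is still in place.

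The facts in this stand, but the inference is weaker.

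- The SUS page is a form for participants to fill in, so the absence of reversal marks is not an error. The Brief Health Literacy Screener, in the same appendix, prints no scoring either, although the first-listed option is unfavourable in its first two questions and favourable in its third.
- The grid was recovered from a PDF. The Need for Cognition table has lost characters at its right edge, so a dropped column cannot be ruled out here. The original form settles the number of options; this text cannot.
- Comparability with published SUS scores cannot be judged from these documents, and the plan does not propose such a comparison.
- An unreversed total would harm the analysis, but it would require the analyst to overlook that every second item from 2 to 10 is a complaint.

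**Conclusion.** No change is needed. What remains is an unstated scoring rule for a named and cited scale. The form can give a valid score: reversing items 2, 4, 6, 8 and 10, rescaling to the response range actually used, and reporting items 11 and 12 separately gives a full 0 to 100 range. That is how a competent analyst would read it, and because the rule acts on stored item answers, it can be applied at analysis with nothing lost.

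The consequences are limited in any case. The ±0.4 SD statement is unaffected. A linear scaling error leaves the Section 6.3 tests as they are. The SUS supplements interview data, the plan excludes formal testing for the primary objective, the comparisons are exploratory in 24 purposively chosen participants, and no decision depends on a score threshold.

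This conclusion assumes that item-level answers are kept and that the analyst checks item direction and the number of response options before computing the score.
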